6.4 Virtual Study Visits

Virtual study visits will be allowable as substitutes for in-person study visits for circumstances precluding in-person visits (e.g., subject has a COVID-19 diagnosis, subject fractures a bone preventing ambulation). Prior to conducting a virtual study visit, the reason for the requested virtual visit should be reviewed and approved by the protocol PI. If a virtual study visit is conducted without prior approval from the protocol PI, it will be considered a protocol deviation.

Note: Visit 5 (Day 8 + 3 days) will always be conducted virtually in Stage 2 without the need for prior approval by the protocol PI.

Virtual study visits will only be allowed for follow-up visits (Day 2, Day 5 ± 2 days, Day 12 + 7 days), the Final Study Visit (Day 30 ± 7 days), or an Early Termination Visit. Virtual study visits will not be allowed for the Screening or Baseline/Dosing Visit. Virtual visits will not be allowed in cases of Unscheduled Visits for safety follow-up for AEs and SAEs related to the study product.

The following will be collected during the virtual study visits:

- Review of systems
- Review of concomitant medications
- Sputum collection for microbiological and PK assessments
- CFRSD (**Stage 2 only**). If subject is ready to produce sputum, prioritize sputum collection over administration of the CFRSD.
- CFQ-R (**Stage 2, Visit 7 [Day 30 ± 7] only**). If subject is ready to produce sputum, prioritize sputum collection over administration of the CFQ-R.
- Clinical assessment of AEs
- Events of special interest [ESIs] (i.e., pulmonary exacerbations), if this visit occurs prior to Visit 5, Day 8 + 3 days (see Section 8.2.2)

A pre-labeled sputum collection kit with instructions and shipping documents will be provided to the subject prior to the visit. Refer to the MOP for further details.

Study procedures that cannot be performed virtually (e.g., vitals, physical examination) will not be considered protocol deviations.

6.5 Unscheduled Study Visits

Unscheduled Study Visits may occur at the investigator's discretion. If an Unscheduled Study Visit occurs, every attempt will be made to collect the following, but it will not be considered a protocol deviation if not collected:

- Review of systems
- Review concomitant medications
- Symptom directed physical examination
- Spirometry*
- Vital signs
- Sputum collection (to be completed after spirometry, as determined necessary by the local investigator to increase sputum production) for microbiological and PK assessments
- Hematology (see Section 7.2.1 for complete list of tests)*
- Clinical chemistry (see Section 7.2.1 for complete list of tests)*
- Liver function tests (see Section 7.2.1 for complete list of tests)*
- CFRSD, preferably before the collection of study data (**Stage 2 only**). If subject is ready to produce sputum, prioritize sputum collection over administration of the CFRSD.
- Clinical assessment of AEs
- Events of special interest [ESIs] (i.e., pulmonary exacerbations), if this visit occurs prior to Visit 5, Day 8 + 3 days (see Section 8.2.2)

**If the visit occurs > 7 days after a scheduled visit. If the visit occurs ≤ 7 days after a scheduled visit, laboratory tests may be collected and spirometry may be performed at the discretion of the local investigator.*

6.6 Protocol Deviations

A protocol deviation is any noncompliance with the clinical trial protocol, GCP, or protocol-specific MOP requirements. Any missing CFQ-R or CFRSD assessments **will not** be considered a protocol deviation. The noncompliance may be either on the part of the subject, the investigator, or the study site staff. As a result of deviations, corrective actions should be developed by the site and implemented promptly. It is the responsibility of the site PI and other study personnel to use continuous vigilance to identify and report protocol deviations. All individual protocol deviations will be addressed in subject study records. All protocol deviations will be collected and stored in a sponsor-determined location. Protocol deviations must be sent to the reviewing IRB/IEC per its guidelines. The site PI and other study personnel are responsible for knowing and adhering to their IRB/IEC requirements.

If an Unscheduled Study Visit occurs, per Section [6.5](#), any assessments/procedures that do not occur will not be considered protocol deviations.

7 DESCRIPTION OF CLINICAL AND LABORATORY EVALUATIONS

7.1 Clinical Evaluations

7.1.1 Research Procedures

- **Demographics:** Demographics will be obtained by subject interview including age, race/ethnicity, and gender.
- **Height and weight measurement:** The subject's height (centimeters) and weight (kilograms) will be measured.
- **Medical history:** The detailed medical history will include completion of a standard template by the study team through a combination of medical record review and subject interview. Medical history will be obtained regarding significant medical disorders of the head, eyes, ears, nose, throat, mouth, cardiovascular system, lungs, gastrointestinal tract, liver, pancreas, kidney, urologic system, nervous system, blood, lymph nodes, endocrine system, musculoskeletal system, skin, and genital/reproductive tract. Medical history will also include a full account of the subject's routine respiratory physiotherapy regimen.
- **Medication history:** A complete medication history will be obtained to include prescription medications, over-the-counter drugs, herbals, vitamins, and supplements the subject has taken. Information regarding any prophylactic systemic or inhaled anti-infective regimens will also be collected. Medication history will be collected both by a review of the medical records as well as by subject interview.
- **Review of systems:** A subject interview will be performed by a study clinician who is licensed to make medical diagnoses. The review of systems will include specific issues with various systems including: general well-being, headaches, vision, hearing, balance, mental health, dizziness, breathing issues, palpitations, nausea, vomiting, diarrhea, abdominal pain, leg swelling, joint swelling, rashes, and urinary symptoms. Refer to the MOP for further details.
- **Vital signs:** The following vital signs will be obtained: systolic and diastolic blood pressures in millimeters of mercury (mmHg), heart rate [beats per minute (BPM)], respiratory rate, and body temperature in degrees Celsius (oral measurement).
- **Physical examination:** Complete physical examination (except for a breast, rectal, and genitourinary examination).
- **Symptom directed physical examination:** A symptom directed physical examination will include the general appearance, lung auscultation (including evaluating for symmetric chest rise, increased work of breathing, and listening for rhonchi or wheezing), and examination of any other body site as indicated by subject symptomatology.

- **Spirometry:** Spirometry will occur prior to required sputum collections, as considered necessary by the local investigator to increase sputum production. Spirometry will be performed according to the standard American Thoracic Society protocol.
- **Cystic Fibrosis Questionnaire-Revised (CFQ-R):** The CFQ-R is a quality of life (QOL) questionnaire designed to measure the impact that CF has on overall health, daily life, and perceived well-being and symptoms.²⁶ The CFQ-R ([Appendix B](#)), contains 50 items and will be administered during study visits for Stage 2 subjects²⁶. For additional details on data collection, refer to the MOP.
- **Cystic Fibrosis Respiratory Symptom Diary (CFRSD):** The CFRSD is a QOL questionnaire, which evaluates the effect of treatment on respiratory infection symptom severity in patients with CF and chronic respiratory infection.²⁷ The CFRSD ([Appendix C](#)) will be collected during study visits for Stage 2 subjects. For additional details on data collection, refer to the MOP.
- Clinical assessment of AEs and ESIs (see Section 8)

7.1.2 Assessment of Concomitant Medications/Treatments Other Than Study Product

Active medications will be reviewed by subject interview and a review of subject medical records. Use of a new medication should prompt evaluation for the presence of a new AE or diagnosis of a new medical condition. Chronic medications, rescue medications, and over-the counter medications are allowed.

7.1.3 Assessment of Subject Compliance with Study Intervention/Investigational Product

Subjects will be directly observed while receiving a single dose of study product or placebo by a member of the study team who is licensed to administer the study product or placebo. Administration data will be recorded in the source and entered into the electronic case report form (eCRF).

7.2 Laboratory Evaluations

7.2.1 Clinical Laboratory Evaluations

Each site will maintain a list of the normal ranges and units of measurement for the laboratory parameters to be determined during this study, and the data and certification number of the laboratory. If the normal ranges change during the course of the study, the site investigator must update this list with the new ranges and effective dates. The normal laboratory reference ranges will also be retained in the regulatory binder at each site.

- **Serum HCG pregnancy test:** A serum HCG pregnancy test will be performed by the local laboratory for all women of childbearing potential at the Screening Visit and the results must be negative prior to treatment assignment/randomization.
- **Urine HCG pregnancy test:** A urine HCG pregnancy test will be performed by the local laboratory for all women of childbearing potential on the day of the Baseline Visit and the results must be negative prior to treatment assignment/randomization.

- **Sputum collection** for microbiological assessments (minimum of 2 mL sample per time point) will be obtained per standard clinical practice, following spirometry, as considered necessary by the local investigator to increase sputum production. Hypertonic saline treatment or other approaches to increase sputum production may be used, as needed, for sputum collection. Approaches for obtaining sputum may include, but are not limited to, inhaled hypertonic saline (e.g., 3%, 7% or 10%), inhaled hypertonic bicarbonate, inhaled mannitol, or spontaneously expectorated sputum. The same approach is recommended, whenever possible, for all sputum collections for a given subject; refer to the MOP for further details. At the Baseline/Dosing Visit, sputum collection will occur prior to administering investigational product/placebo and at 2 hours post completion of administering study product/placebo and flushing the IV line (\pm 1 hour). Samples will be collected by the local laboratory and will be sent to a central laboratory for analysis. Refer to the MOP for details.
- **Clinical chemistries** will be measured at the local laboratory and include serum creatinine, blood urea nitrogen, glucose, sodium, potassium, chloride, bicarbonate, and calcium.
- **Hematology** will be measured at the local laboratory and include complete blood count with red blood cell (RBC) count, hemoglobin, hematocrit, total white blood cell (WBC) count with differential counts, and platelet count.
- **Liver function tests** will be measured at the local laboratory and include AST, ALT, alkaline phosphatase, total bilirubin, lactate dehydrogenase, albumin, and total protein. Only AST, ALT, and total bilirubin are necessary at Screening.

7.2.2 Research Assays

- **Serum PK** studies (~3 mL sample of whole blood per time point) will be conducted per the directions in the MOP. At the Baseline/Dosing Visit, blood will be collected at any time (on the same calendar day) prior to the start of investigational product/placebo administration, and at 30 min, 1 hour, 1.5 hours, 2 hours, 2.5 hours, 3 hours, and 3.5 hours post completion of administering study product and flushing the IV line (all time points are \pm 10 min). At Follow-up Visit 3 (Day 2), the PK serum sample will be collected once at any time, the time must be recorded, during the in-person visit. Samples will be collected by the local laboratory and sent to a central laboratory for analysis.
- **Sputum PK** studies (minimum of 2 mL sample per time point) will be obtained per standard clinical practice, following spirometry, as considered necessary by the local investigator to increase sputum production. Hypertonic saline treatment or other approaches to increase sputum production may be used, as needed, for sputum collection. Approaches for obtaining sputum may include, but are not limited to, inhaled hypertonic saline (e.g., 3%, 7% or 10%), inhaled hypertonic bicarbonate, inhaled mannitol, or spontaneously expectorated sputum. The same approach is recommended, whenever possible, for all sputum collections for a given subject, refer to the MOP for further details. At the Baseline/Dosing Visit, sputum collection will occur prior to administering investigational product/placebo, and at 2 hours post completion of administering study product/placebo and flushing the IV line (\pm 1 hour).

Samples will be collected by the local laboratory and will be sent to a central laboratory for analysis. Refer to the MOP for details.

- ***P. aeruginosa* colony counts** will be performed by the central lab using quantitative bacterial cultures on sputum specimens collected from the time of bacteriophage administration through Day 30 ± 7 days. Quantities of sputum (10 mg) will be measured precisely and added to 1 mL Sputolysin mucolytic agent to liquefy the sample. The liquefied sample will be diluted sequentially and plated onto MacConkey agar and Sheep's Blood Agar Plates using a 1 μ L loop for each replicate. Colonies will be counted on the highest dilution in which individual colonies can be enumerated and colony counts adjusted appropriately based on the dilution factor and the mass of the sample to determine the true concentration of *P. aeruginosa*. Colonies representing different morphotypes will be definitively identified using MALDI-TOF to ensure that each enumerated colony type represents *P. aeruginosa*. Refer to the MOP for additional details.
- ***P. aeruginosa* susceptibility to bacteriophages** may be performed by the central lab on *P. aeruginosa* isolates in sputum cultures, depending on sample availability.

7.2.2.1 Laboratory Specimen Preparation, Handling, and Storage

Specific instructions are included in the MOP.

7.2.2.2 Laboratory Specimen Shipping

Specific instructions are included in the MOP.

7.2.3 Secondary Analysis of Stored Specimens and Data

The information and samples/specimens collected for this study may be used for future, currently unknown, research. The secondary research may include, but is not limited to additional work on bacteriophage treatment; cystic fibrosis; and infections of the blood, lung, skin, or other parts of the body. The research may include, but is not limited to further investigating bacteriophage susceptibility testing, serum neutralizing antibodies, whole genome sequencing the *P. aeruginosa* isolates, and changes to the respiratory microbiome. No human genetic testing or sequencing of human DNA will be performed using the samples/specimens collected.

8 ASSESSMENT OF SAFETY

8.1 Assessing and Recording Safety Parameters

This study will assist in enhancing the understanding of the safety and microbiological activity of IV bacteriophage therapy in clinically stable CF subjects with *P. aeruginosa* in expectorated sputum. Safety will be assessed by the frequency and severity of AEs.

8.1.1 Adverse Events (AEs)

International Council for Harmonisation (ICH) E6 defines an AE as any untoward medical occurrence in a patient or clinical investigation subject administered a pharmaceutical product regardless of its causal relationship to the study treatment. The FDA defines an AE as any untoward medical occurrence associated with the use of a drug in humans, whether or not considered drug related.

An AE can therefore be any unfavorable and unintended sign (including an abnormal laboratory finding), symptom, or disease temporally associated with the use of medicinal (investigational) product. The occurrence of an AE may come to the attention of study personnel during study visits and interviews of a study recipient presenting for medical care, or upon review by a study monitor.

All AEs of grade 2 or higher including lab abnormalities, abnormal clinical finding, and including local (infusion site) and systemic (subjective and quantitative) reactions, will be captured on the appropriate data collection form and eCRF regardless of causality or clinical significance.

Grade 1 AEs including lab abnormalities, abnormal clinical finding, and including local (infusion site) and systemic (subjective and quantitative) reactions, will be captured on the appropriate data collection form and eCRF only if assessed by the treating clinician as related to the study product.

Information to be collected for AEs includes event description, date of onset, assessment of severity, relationship to study product, potential alternate etiologies (assessed only by those with the training and authority to make a diagnosis and listed on the Form FDA 1572 as an investigator), date of resolution, seriousness, and outcome. AEs occurring during the trial collection and reporting period will be documented appropriately regardless of relationship.

Any medical condition that is present at the time that the subject is screened will be considered as baseline and not be reported as an AE. However, if the frequency and/or severity of any pre-existing medical condition increases, it should be recorded as an AE.

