8.1.1.1 Adverse Events Grading

AEs, including laboratory and clinical symptoms, will be graded for severity according to the Common Terminology Criteria for Adverse Events (CTCAE) Version 5.0, November 2017 (https://ctep.cancer.gov/protocoldevelopment/electronic_applications/ctc.htm#ctc_50) and

assessed for relationship to study product. AEs characterized as intermittent require documentation of onset and duration of each episode. The start and stop date of each reported AE will be recorded on the appropriate data collection form and eCRF.

Relationship to Study Product: The assessment of the AE's relationship to study product will be performed by a delegated, licensed study clinician listed on the Form FDA 1572. The assessment will be part of the documentation process. Whether the AE is related to the study product or not, is not a factor in determining what is or is not reported in this trial. If there is any doubt as to whether a clinical observation is an AE, the event should be reported.

In a clinical trial, the study product must always be suspect. The AEs will be assessed for relationship to the study product using the terms "related" or "not related":

- Related – There is a reasonable possibility that the study product caused the AE. Reasonable possibility means that there is evidence to suggest a causal relationship between the study product and the AE.
- Not Related – There is not a reasonable possibility that the administration of the study product caused the event.
- Note: Pulmonary exacerbations are known to occur in individuals with CF with some frequency and will be considered **unrelated** to the study drug if they occur after Visit 5, Day 8 + 3 days. If a pulmonary exacerbation occurs during the ESI collection period (Baseline/Dosing through Visit 5), it may be considered related, at the discretion of the local investigator.

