8.5 Procedures to be Followed in the Event of Abnormal Laboratory Test Values

Any Grade 2 or higher abnormal laboratory value will be reported as an AE, regardless of the relationship to the study product or clinical significance. Grade 1 laboratory abnormalities will be reported as AEs if assessed by the investigator as related to the study product. Laboratory abnormalities reported as AEs will be followed until the abnormality stabilizes, normalizes or returns to a baseline level, whichever comes first, at the discretion of the investigator.

In the approach to grading laboratory values, if the Lower Limit of Normal (LLN) entered at the site falls within CTCAE defined graded values, the CTCAE ranges will be used to grade an AE, rather than using local laboratory ranges for determining normal and abnormal laboratory values.

Intermittent abnormal laboratory values such as electrolyte abnormalities or blood glucose levels that are part of the same clinical diagnosis (e.g., uncontrolled diabetes) can be recorded once with the highest grade for each fluctuating AE (Grade 2 or higher for this trial), including the start and stop dates of the intermittent syndrome. If the event has a clear resolution for a duration of at least 48 hours and then recurs, it should be treated as a separate AE. An AE resolution is defined as return to pre-treatment status or baseline for duration of more than 48 hours.

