### 9.3.2. Unsolicited Adverse Events

The proportion of subjects reporting at least one unsolicited AE will be summarized by MedDRA SOC, HLT, and PT and by treatment group. Denominators for proportions are the number of subjects in the Safety Population in each treatment group.

Unsolicited AEs by subject will be presented in [Listing 17](#).

The following summaries for unsolicited AEs will be presented:

- Overall summary of AEs ([Table 40](#)).
- AEs occurring in 5% of subjects in any treatment group are summarized by MedDRA SOC, HLT, and PT and by treatment group in Stage 1 ([Table 41](#)), Stage 2a ([Table 42](#)), and Stage 2a and 2b ([Table 43](#)).
- Subject incidence and total frequency of unsolicited AEs by MedDRA SOC, HLT, and PT and by treatment group with 95% CI, calculated using an exact Clopper-Pearson confidence interval in Stage 1 ([Table 46](#)), Stage 2a ([Table 47](#)), and Stage 2a and 2b ([Table 48](#)).
- Summary of unsolicited AEs by severity, relationship to study product, MedDRA SOC, HLT, and PT and by treatment group in Stage 1 ([Table 49](#)), Stage 2a ([Table 50](#)), and Stage 2a and 2b ([Table 51](#)).
- Summary of TEAEs, on-therapy SAEs, and AEs leading to discontinuation by MedDRA PT in Stage 1 ([Table 52](#)), Stage 2a ([Table 53](#)), and Stage 2a and 2b ([Table 54](#)). TEAEs are any AEs that were not present before the first dose of study product or were present before the first dose of study product and increased in severity during the treatment period. On-therapy SAEs are any SAEs occurring during or after the infusion of bacteriophage/placebo product.
- Summary of fatal on-therapy SAEs by MedDRA PT and treatment group ([Table 55](#)).
- Bar chart frequency of AEs by severity, MedDRA SOC, and treatment group in Stage 1 ([Figure 14](#)), Stage 2a ([Figure 15](#)), and Stage 2a and 2b ([Figure 16](#)).
- Bar chart incidence of AEs by severity, MedDRA SOC, and treatment group in Stage 1 ([Figure 17](#)), Stage 2a ([Figure 18](#)), and Stage 2a and 2b ([Figure 19](#)).

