Treatment group order: All subjects,  $4 \times 10^7$  PFU Dose,  $4 \times 10^8$  PFU Dose,  $4 \times 10^9$  PFU Dose, Placebo.]

Treatment Group	MedDRA System Organ Class	MedDRA High Level Term	MedDRA Preferred Term	N	n (%)	95% CI a	Number of Events
All Subjects (N=X)	Any SOC	Any HLT	Any PT	x	x (x)	xx, xx	x
	[SOC 1]	Any HLT	Any PT	x	x (x)	xx, xx	x
		[HLT 1]	Any PT	x	x (x)	xx, xx	x
			[PT 1]	x	x (x)	xx, xx	x
	[SOC 2]	Any HLT	Any PT	x	x (x)	xx, xx	x
		[HLT 1]	Any PT	x	x (x)	xx, xx	x
			[PT 1]	x	x (x)	xx, xx	x
4 $\times$ 10  PFU Dose (N=X)	...		...	x	x (x)	xx, xx	x
...	...		...	x	x (x)	xx, xx	x
Placebo (N=X)	...		...	x	x (x)	xx, xx	x

Notes: N=number of subjects in the Safety Population in the specified Treatment Group.

A subject is only counted once per PT per treatment group and study part.

aExact Clopper-Pearson Confidence Interval.

**Table 47: Summary of Unsolicited Adverse Events by MedDRA System Organ Class, Preferred Term, and Treatment Group, Stage 2a – Safety Population****Table 48: Summary of Unsolicited Adverse Events by MedDRA System Organ Class, Preferred Term, and Treatment Group, Stage 2a and 2b – Safety Population**

**Table 49: Unsolicited Adverse Events by MedDRA System Organ Class, High Level Term, Preferred Term, Maximum Severity, Relationship, and Treatment Group, Stage 1 – Safety Population**[Implementation Note: Treatment group order: All subjects,  $4 \times 10^7$  PFU Dose,  $4 \times 10^8$  PFU Dose,  $4 \times 10^9$  PFU Dose, Placebo.]

Treatment Group	MedDRA System Organ Class	MedDRA High Level Term	MedDRA Preferred Term	Severity	Related n (%)	Not Related n (%)	Total n (%)
All Subjects (N=X)	Any SOC	Any HLT	Any PT	Any Severity	x (%)	x (%)	x (%)
				Mild	x (%)	x (%)	x (%)
				Moderate	x (%)	x (%)	x (%)
				Severe	x (%)	x (%)	x (%)
	[SOC 1]	Any HLT	Any PT	Any Severity	x (%)	x (%)	x (%)
				...	x (%)	x (%)	x (%)
			[PT 1]	Any Severity	x (%)	x (%)	x (%)
				...	x (%)	x (%)	x (%)
$4 \times 10^7$ PFU Dose (N=X)	Any SOC		Any PT	Any Severity	x (%)	x (%)	x (%)
...	...		...	...	x (%)	x (%)	x (%)
Placebo (N=X)	...		...	...	x (%)	x (%)	x (%)

Notes: N=Number of subjects in the Safety Population in each Treatment Group.

Subjects are only counted once per PT and treatment group, in the highest reported severity.

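### Grade 1 adverse events are recorded only when judged related, under contradictory protocol text, but the SAP tabulates any-severity incidence and a Mild/Not Related cell without saying so

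*Protocol*

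**What the plan says.** Protocol 8.1.1 sets two capture rules by grade. AEs of Grade 2 or higher "will be captured on the appropriate data collection form and eCRF regardless of causality or clinical significance". Grade 1 AEs "will be captured on the appropriate data collection form and eCRF only if assessed by the treating clinician as related to the study product". Protocol 8.5 repeats the second rule for laboratory values: "Grade 1 laboratory abnormalities will be reported as AEs if assessed by the investigator as related to the study product".

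Two other sentences point the opposite way. Later in 8.1.1: "AEs occurring during the trial collection and reporting period will be documented appropriately regardless of relationship". And 8.1.1.1 says that relationship to study product "is not a factor in determining what is or is not reported in this trial".

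The SAP does not carry the grade-dependent rule forward. Section 9.3 puts every reported AE into the summaries. Section 9.3.2 states: "The proportion of subjects reporting at least one unsolicited AE will be summarized by MedDRA SOC, HLT, and PT and by treatment group", with no severity restriction. Table 40 has a row for subjects with any AE. Tables 41-43, 46-48 and the treatment-emergent block of Tables 52-54 count AEs of any grade, and Figures 14-19 split them by severity. Tables 49-51 cross Mild, Moderate and Severe with Related, Not Related and Total. The Table 49 notes give a counting rule, "Subjects are only counted once per PT and treatment group, in the highest reported severity", but none of these shells says that unrelated Grade 1 events were not collected.

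**The concern.** Describing safety is a primary objective, and Protocol 8.1 assesses it by the frequency and severity of AEs. The any-severity tables would add a complete count (Grade 2 or higher) to one selected on a causality opinion (Grade 1), and present the sum as incidence. A reader of Tables 49-51 could take a blank or near-blank Mild/Not Related cell as an observation that mild events were almost all product-related, when the cell reflects what was collected.

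The contradictory wording adds a second problem. A site following 8.1.1 and 8.5 omits mild unrelated events; a site following 8.1.1.1 records them. The trial may use up to 20 sites, and SAP 6.7 pools sites without adjustment, so the Grade 1 data could mix two rules that nobody can separate afterwards.

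**Working it through.** The documents state no AE rate and no related share, so there is no planned figure to reproduce. The first step is logical; the other two use assumed values to show size.

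**Step 1. Capture rule against the Table 49 cells.** The laboratory shells (for example Table 63) equate Mild with Grade 1.

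| Cell | Recorded under Protocol 8.1.1? |
|---|---|
| Mild, Related | Yes |
| Mild, Not Related | No, unless it enters by another route |
| Moderate or Severe, Related | Yes |
| Moderate or Severe, Not Related | Yes |

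Mild Total therefore equals, or nearly equals, Mild Related.

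The other routes are the 8.1.1.1 wording; the condition behind a new anti-pseudomonal antibiotic, which Protocol section 6 reports as an AE with no grade or relatedness condition; and 8.3.1, which captures unrelated serious AEs.

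**Step 2. Related share, by events.** Let a = mild related, b = mild unrelated, c = Grade 2+ related, d = Grade 2+ unrelated. With none of the other routes in play:

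- Mild related share: true a/(a+b); recorded a/a.
- Overall related share: true (a+c)/(a+b+c+d); recorded (a+c)/(a+c+d).
- Events lost: b.

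| Assumed a, b, c, d | Mild share, true to recorded | Overall share, true to recorded | Events, true to recorded |
|---|---|---|---|
| 2, 8, 1, 6 | 2/10 = 20% to 100% | 3/17 = 18% to 3/9 = 33% | 17 to 9 |
| 1, 20, 1, 8 | 1/21 = 5% to 100% | 2/30 = 7% to 2/10 = 20% | 30 to 10 |
| 5, 5, 3, 7 | 5/10 = 50% to 100% | 8/20 = 40% to 8/15 = 53% | 20 to 15 |
| 0, 10, 0, 6 | 0% to undefined | 0% to 0% | 16 to 6 |

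The mild share is fixed at 100% whenever any mild event is recorded. The overall share rises if there is any related event, but is not fixed.

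**Step 3. Any-AE incidence, by subject.** Let u, r and g be a subject's probability of at least one mild unrelated, mild related and Grade 2+ AE, taken as independent.

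- True: 1 − (1−u)(1−r)(1−g). Recorded: 1 − (1−r)(1−g). Shortfall: u(1−r)(1−g).
- Assumed ranges: u 0.2 to 0.6, r 0.05 to 0.15, g 0.2 to 0.4. N = 25 is the Stage 2 maximum per arm in Protocol 10.2.

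| u, r, g | True | Recorded | Subjects of 25 |
|---|---|---|---|
| 0.2, 0.05, 0.2 | 1 − 0.8×0.95×0.8 = 39% | 1 − 0.95×0.8 = 24% | 9.8 vs 6.0 |
| 0.2, 0.15, 0.4 (smallest gap) | 1 − 0.8×0.85×0.6 = 59% | 1 − 0.85×0.6 = 49% | 14.8 vs 12.2 |
| 0.6, 0.05, 0.2 (largest gap) | 1 − 0.4×0.95×0.8 = 70% | 24% | 17.4 vs 6.0 |
| 0.6, 0.15, 0.4 | 1 − 0.4×0.85×0.6 = 80% | 49% | 19.9 vs 12.2 |

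Over the whole grid, true incidence of 39% to 80% is shown as 24% to 49%. Grade 2+ counts do not change in any row.

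**The case against.** The strongest reply is that limiting capture of mild events is a legitimate choice, stated in two places, and that the SAP Preface sends readers to the protocol for operational detail. Table 44 already gives Grade 2 or higher treatment-emergent AEs by arm with exact intervals, and Table 45 the difference from placebo. Much Grade 1 information also appears elsewhere with no causality filter: the laboratory and vital-sign severity tables have Grade 1 columns, and Listings 22 and 23 show examination and review-of-systems findings with a field for whether each was reported as an AE. All of this stands, and it limits the damage. It does not caption the affected tables, and it leaves laboratory tables showing Grade 1 abnormalities that the AE tables omit without explanation.

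A reader might go further than the documents allow:

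- *That every recorded AE will look product-related.* No. Unrelated Grade 2+ events are captured, so only the mild row is affected in this way.
- *That Mild/Not Related is a strict zero.* Not established. The other routes could fill it partly and unevenly, and the shell shows only a placeholder.
- *That the comparison between arms is biased towards or against phage.* In Stage 2 the assessor is blinded, so the filter is applied without knowledge of arm. Stage 1 is open-label, but it has six subjects, all on active product, so it contains no placebo contrast to distort.
- *That Table 40 fails as a whole.* Its related-AE rows are untouched, since related events are captured at every grade. The any-AE row is the one clearly affected.

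**Conclusion.** Wrong as written, in two linked respects. The protocol gives incompatible instructions on whether unrelated Grade 1 events are recorded, and the SAP tabulates the result as if Grade 1 were fully ascertained. If 8.1.1 is followed, any-severity incidence is understated, the mild row cannot inform on relatedness, and the Mild/Not Related cell cannot be read as observed. If sites differ, the cell is partly filled and harder still to interpret.

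The direction follows from the capture rule. The size (39% to 80% shown as 24% to 49%) rests on assumed rates, on independence between event types and on no entry by other routes. The consequence is confined to descriptive safety displays; the Grade 2 or higher primary endpoint in Tables 44-45 does not depend on Grade 1 capture.

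**What to change.** 1. Reconcile Protocol 8.1.1, 8.1.1.1 and 8.5 to a single stated capture rule for Grade 1 AEs.
2. In SAP Tables 40-43 and 46-54 and Figures 14-19, label the totals *Grade 2 or higher plus related Grade 1* and show the Grade 2 or higher subtotal beside them. Keep the combined total: replacing it with Grade 2 or higher alone would drop related Grade 1 events that were collected and would largely repeat Table 44.
3. In Tables 49-51, print *not systematically collected* instead of 0 for Mild/Not Related, and list any such events that entered by another route.

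The cost is a protocol clarification plus table-shell and footnote edits. No new data are collected.
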